## 2. Protocol Synopsis

Patient Exposure Study	
Study Objective(s)	Primary Objective: to calculate the radiation-absorbed dose of Technetium-99m macroaggregated albumin (Tc-99m MAA) to the whole body and to potential irradiated non-liver critical organs.
Patient Population	Patients who are being evaluated for TheraSphere administration.
Study Product	Tc-99m macroaggregated albumin
Study Design	
Post-market prospective, single-arm, open-label, observational study. Patients will be required to provide written informed consent prior to any study procedures being conducted. Patients who provide written informed consent, fulfill all the inclusion criteria and meet none of the exclusion criteria will be considered enrolled in the study.
 
Patients who are enrolled in the study will have 3 images taken after Tc-99m MAA injection, with the final image occurring between 18 and 24 hours after Tc-99m MAA injection.
 
Planned Number of Patients	A total of five patients will be enrolled in the study.
Planned Number of Sites / Countries	The study will be conducted at up to three clinical study sites in the US.

## Patient Exposure Study

Primary Endpoints	Mean absorbed dose (Gy) and activity (Bq) will be summarized for the whole body and for critical non-liver organs (including whole body effective dose).
Follow-up Schedule	
At a minimum, all patients will be evaluated at the following timepoints:
 
 
• Immediately following Tc-99m MAA injection
 
• 4 hours <math>\pm</math> 2 hours after Tc-99m MAA injection
 
• <math>\geq</math> 18 hours after Tc-99m MAA injection but <math>\leq</math> 24 hours after Tc-99m MAA injection
 
 
At each evaluation timepoint, the following images will be performed:
 
 
• Immediately following Tc-99m MAA injection: Single Photon Emission Computed Tomography in conjunction with Computed Tomography (SPECT-CT)
 
• All other images: Single Photon Emission Computed Tomography (SPECT)
 
 
The start of the study for each eligible patient will be immediately after signed written informed consent. The study will be considered complete after five patients have completed three post-Tc-99m MAA imaging assessments.

Study Duration	Enrollment is expected to be completed within 24 months; therefore, the total study duration is estimated to be 24 months.
Participant Duration	The study duration for each subject is expected to be up to 24 hours.
Inclusion Criteria	
 
1. Patients 21 years and older
 
2. Patient written informed consent
 
3. Patients who receive Tc-99m MAA while being evaluated for TheraSphere treatment
 

Exclusion Criteria	
 
1. Patients who are contraindicated for TheraSphere treatment
 
2. Patients who are contraindicated for Tc-99m MAA per the applicable Package Insert
 
3. Patients who do not receive Tc-99m MAA during pre-treatment Y-90 mapping
 

## Patient Exposure Study

### Statistical Methods

Statistical Test Method	No formal hypothesis testing is proposed for the study assessment. Analyses and summaries will be descriptive.
--------------------------------	--

## 4. Introduction

### 4.1. *Background and Study Rationale*

TheraSphere is a Y-90 glass microsphere therapy for Selective Internal Radiation Therapy (SIRT) in hepatocellular carcinoma (HCC). The treatment goal of SIRT is to selectively target and deliver a tumoricidal radiation dose to tumors within the liver, while maintaining an acceptable radiation dose to the normal liver tissue.

TheraSphere is administered through the hepatic artery which supplies blood to the hepatic tumors. The mean tissue penetration of the beta energy from the Y-90 in the microspheres is approximately 2.5 mm, with a maximum range up to 11 mm. Cancer cells adjacent to the embedded microspheres are killed while the nearby hepatic parenchyma and tissues in adjacent organs are generally spared the destructive effects of the beta radiation.

The United States Food and Drug Administration (FDA) approved the use of TheraSphere to treat unresectable HCC on March 17, 2021.

Prior to administration of TheraSphere, hepatic arteriography and Technetium-99m macroaggregated albumin (Tc-99m MAA) scanning are performed to detect extrahepatic shunting to the lung or the gastrointestinal tract.

This study is being conducted, at the request of the FDA, to provide data to calculate the radiation-absorbed dose of Tc-99m MAA to the whole body and to potential irradiated non-liver critical organs.

## 5. Study Product Description

Lung perfusion scintigraphy with Tc-99m MAA is an important diagnostic tool in SIRT planning. Tc-99m MAA is utilized as a TheraSphere surrogate.

There are several Tc-99m MAA imaging agents that have been approved by the FDA that can be used for TheraSphere pre-treatment mapping. The specific brand of Tc-99m MAA imaging agent that is used is at the discretion of the physician.

Several studies have examined the biodistribution of Tc-99m MAA as used in TheraSphere pre-treatment planning procedures. Bailey et al published a retrospective case series review of 70 HCC patients and examined extrahepatic uptake using combined planar and SPECT/CT imaging (1). Results showed the largest uptake was seen in the renal cortex, salivary glands, thyroid gland and gastric mucosa amongst 70 patients (100%), 23 patients (33%), 23 patients (33%) and 32 patients (46%), respectively. Lesser uptake was noted in other organs in fewer patients. This extrahepatic deposition is thought to be a result of deposition of Tc-99m MAA breakdown products such as free Tc-99m-pertechnetate which is released over time (1) (2) (3). In the gastric mucosa and thyroid gland, free 99mTc-pertechnetate deposition is visualized as a diffuse pattern and in the stomach is distinguishable from non-target Tc-99m MAA delivery and does not represent non-target administration or a pathologic concern (3) (4). Uliel et al suggested that using a high labelling efficiency Tc-99m-pertechnetate and minimizing the time interval between radiotracer injection and imaging time reduces the amount of nonspecific background activity (3).

In clinical practice, there is typically a delay between Tc-99m MAA injection and imaging during which dissociation of the Tc-99m MAA occurs. Grosser et al found that there was a time-dependent significant release of free 99mTc from the liver over a 24-hour time period after examining scans taken at 1, 5 and 24 hours after intraarterial Tc-99m MAA injection (5). The biexponential decay curve can be best described as: T half-life, fast = 7.9 hours, T half-life, slow =22.4 hours; adjusted  $R^2=0.77$ . The authors therefore recommended that liver perfusion scintigraphy with Tc-99m MAA be performed no later than four hours after injection. De Gersem et al did a similar study performing whole body scans at < 1 hour, between 1 and 4 hours, and > 4 hours post Tc-99m MAA injection (2). They found higher levels of radioactivity in the lung (extrahepatic deposition) in the > 4 hour scans than in the < 1 hour scans. This overestimation has clinical relevance as the authors conclude that based on > 4 hour scan results, several patients would have been excluded from receiving radioembolization. The longer imaging is delayed post radiotracer injection, the more free Tc-99m is released. The same logic can be applied to extrahepatic activity seen on imaging post Tc-99m MAA injection. Indeed, Bailey et al did not note any correlation between extrahepatic uptake and time to imaging however their mean interval was only 92 minutes (1).

In summary, several authors have described the reasons for extrahepatic organ uptake of Tc-99m MAA degradation products as visualized on imaging. Presence of radiotracer in these organs originates from Tc-99m MAA degradation products and does not pose a clinical concern (3). Keeping the time interval between radiotracer injection and imaging as short as possible limits the distribution of radiotracer degradation products to extrahepatic tissue (1).

## 6. Study Objective

The objective of this study is to provide data to calculate the radiation-absorbed dose of Tc-99m MAA to the whole body and to potential irradiated non-liver critical organs.

## 7. Study Design

The TheraSphere Post-Approval Study is a post-market, prospective, single-arm, open-label, observational study to support the use of TheraSphere for the treatment of hepatocellular carcinoma.

### 7.1. Scale and Duration

[figure not shown]
This study is planned to be conducted at up to 3 clinical study sites in the United States. Five patients will be enrolled in the study.

A patient is considered enrolled once an informed consent form has been signed, and all inclusion and no exclusion criteria have been met.

If the patient is found to not meet the inclusion criteria, the patient should not be included in the study.

Patients enrolled in the study will have 3 images taken after Tc-99m MAA injection. The final image will occur between 18 and 24 hours after Tc-99m MAA injection.

Enrollment is expected to be completed within 24 months; therefore, the total study duration is estimated to be 24 months.

**Figure 7.1-1: TheraSphere Post-Approval Study Design**

## 7.2. *Justification for the Study Design*

This post-market study is being conducted at the direction of the FDA. Eligible study patients, after discussion and agreement with their treating physician, will be undergoing evaluation for the delivery of TheraSphere for the treatment of HCC. This study will provide data on the pre-Y-90 radiation-absorbed dose risk of Tc-99m MAA to the whole body and to potential irradiated non-liver critical organs.

## 8. Subject Selection

### 8.1. *Study Population and Eligibility*

The intended population for the TheraSphere Post-Approval study is patients with HCC who are undergoing evaluation to assess eligibility for TheraSphere treatment.

### 8.2. *Inclusion Criteria*

Subjects who meet all of the following criteria (see Table 8.2-1) may be given consideration for inclusion in this clinical investigation, provided no exclusion criterion (see Section 8.3) is met.

**Table 8.2-1: Inclusion Criteria**

Inclusion Criteria	1. Patients 21 years and older 2. Written informed consent 3. Patients who receive Tc-99m MAA while being evaluated for TheraSphere treatment
--------------------	---

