**Table 8.3-1: Exclusion Criteria**

Exclusion Criteria	1. Patients who are contraindicated for TheraSphere treatment 2. Patients who are contraindicated for Tc-99m MAA per the applicable Package Insert 3. Patients who do not receive Tc-99m MAA during pre-treatment Y-90 mapping
---------------------------	---

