### **10.2.1. Strategies for Recruitment and Retention**

The intended population for this study are patients who are undergoing evaluation for the use of TheraSphere to treat HCC. Patients may be recruited through the Investigator's practice or referring physicians. Any information disseminated to potential patients (e.g. advertisements, pamphlets, posters) must be approved by the investigational center's IRB prior to use.

Every effort must be made by the site to collect patient data per the Data Collection Schedule in Section 10.1.

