3 PROTOCOL SUMMARY

TheraSphere is a Y-90 glass microsphere therapy for Selective Internal Radiation Therapy (SIRT) in hepatocellular carcinoma (HCC). Its treatment goal is to selectively target and deliver a tumoricidal radiation dose to tumors within the liver, while maintaining an acceptable radiation dose to the normal liver tissue. The United States Food and Drug Administration (FDA) approved the use of TheraSphere to treat unresectable HCC on March 17, 2021.

Prior to administration of TheraSphere, hepatic arteriography and Technetium-99m macroaggregated albumin (Tc-99m MAA) scanning are performed to detect extrahepatic shunting to the lung or the gastrointestinal tract. At the request of the FDA, the TheraSphere Post-Approval Study (PAS) is being conducted to evaluate the pre-Y-90 radiation-absorbed dose risk of Tc-99m MAA to the whole body and to potential irradiated non-liver critical organs.

TheraSphere PAS is a post-market prospective, single-arm, open-label, observational study. Its primary objective is to calculate the radiation-absorbed dose of Tc-99m MAA to the whole body and to non-liver critical organs. The study will be conducted at up to three clinical study sites in the US, and plans to enroll a total of five patients who are being evaluated for TheraSphere administration.

Study subjects will be required to provide written informed consent prior to any study procedures being conducted. Those who provide written informed consent, fulfill all the inclusion criteria and meet none of the exclusion criteria will be considered enrolled in the study. Subjects enrolled in the study will have 3 images taken after Tc-99m MAA injection: immediately after the injection, 4 hours (within ± 2 hours window) after the injection, and between 18 and 24 hours after Tc-99m MAA injection (Figure 1.1).

[figure not shown]

Figure 1: TheraSphere Post-Approval Study Design

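### Does the lack of a named HCC diagnosis in the eligibility criteria, when other sections describe an HCC population, call for a change to the plan?

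*Protocol*

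**What the plan says.** Three protocol sections describe an HCC population.

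- Section 8.1: "The intended population for the TheraSphere Post-Approval study is patients with HCC who are undergoing evaluation to assess eligibility for TheraSphere treatment".
- Section 7.2 says of the study's eligible patients that they "will be undergoing evaluation for the delivery of TheraSphere for the treatment of HCC".
- Section 10.2.1: "The intended population for this study are patients who are undergoing evaluation for the use of TheraSphere to treat HCC".

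The operative lists name no diagnosis. Inclusion requires age 21 or older, written consent, and (third criterion) "Patients who receive Tc-99m MAA while being evaluated for TheraSphere treatment". The first exclusion is "Patients who are contraindicated for TheraSphere treatment". The other two exclusions concern a contraindication to Tc-99m MAA and not receiving it at mapping. The population line of the synopsis reads "Patients who are being evaluated for TheraSphere administration", and SAP section 3 says the study "plans to enroll a total of five patients who are being evaluated for TheraSphere administration".

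Enrollment (Protocol 9.1 and 10.2) is consent plus these criteria. ITT (Protocol 11.3.1, SAP 5.1) is enrolled patients who meet eligibility, and it is the set for all analyses. SAP 7.1 derives months since HCC diagnosis, and Listing 16.2.1.3 prints the HCC diagnosis date for each subject.

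**The concern.** If the criteria tables alone decide who enters, a patient without HCC who is being worked up for TheraSphere may satisfy all six and join the ITT set. Section 8.2 says that those who meet the criteria "may be given consideration for inclusion in this clinical investigation", which sounds like discretion. However, Protocol 11.3.2 and SAP 5.2 commit to including every consecutive eligible patient who consents, so discretion is not a dependable filter.

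With five patients planned, one such patient would be a visible share of each mean. The completion rule in Protocol 9.3 could be met with four HCC patients. The SAP has no rule for a subject without an HCC date, and because SAP section 10 prints missing values as blanks, Listing 16.2.1.3 alone would not separate no HCC from an unrecorded date. At stake is which population the reported doses describe, in a study done at the FDA's request.

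**Working it through.** There is no sample-size calculation to reproduce: Protocol 11.2 and SAP 6.2 state that five patients are required without a formal derivation. The check is mainly a comparison of passages, with some simple arithmetic.

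**1. Is the mismatch real?** Yes. Protocol 7.2, 8.1 and 10.2.1 name HCC. The six criteria, the synopsis population line and the enrollment sentence in SAP 3 do not.

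**2. Can a non-HCC patient clearly meet the criteria?** This is not settled.

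- The subject of the sentence in 7.2 is the study's eligible patients, so it ties eligibility to HCC treatment.
- The heading of 8.1 couples population with eligibility.
- Protocol 4.1 and SAP 3 introduce TheraSphere as a therapy in HCC and mention only that approved use, so being evaluated for TheraSphere can fairly be read as being evaluated for HCC treatment.
- Whether the first exclusion bars a non-HCC patient depends on product labeling that is not in the documents.
- SAP revision B removed an IFU requirement to follow a protocol eligibility change made to support enrollment. The removed wording is not shown, so it cannot be tied to diagnosis. The current SAP has an HCC history variable.

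The most the text supports is that such a patient might be enrolled.

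**3. Would it be noticed?** Medical history is collected at screening (Protocol 10.4) and summarized (11.4.1). The HCC date is listed per subject (Listing 16.2.1.3). SAP 5 counts missing data, Protocol 12.1 provides for queries, and monitors review source documents (19.1). Among about five rows, a blank HCC date would stand out and could be queried.

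**4. Arithmetic.** The weight of one patient in a mean of n is 1/n.

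| n evaluable | weight of one patient |
|---|---|
| 4 | 1/4 = 25.0% |
| 5 | 1/5 = 20.0% |
| 6 | 1/6 = 16.7% |

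This weight is the same for any patient with any characteristic. It also holds at 20% only if exactly five are evaluable: Protocol 9.3 ends the study at five imaging completers, while ITT counts all eligible enrolled patients. A shift in the mean needs a dose difference as well as a weight. Replacing one HCC patient's dose by one that differs by d moves a five-patient mean by d/5. The documents give no value for d and no count of non-HCC candidates, so neither the size nor the chance of a shift can be derived.

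**5. Is the result recoverable?** Yes. Listing 16.2.2.3 gives activity and dose by organ for each subject. If the five-patient mean is M and the patient in question has value x, the mean of the other four is (5M − x)/4.

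**6. What would a change do?** Naming HCC in the criteria would only write down the existing meaning if HCC is already implied. If it is not implied, it would narrow entry to a study whose eligibility was altered to help enrollment, where low enrollment is a listed termination reason (Protocol 20.1.1). Widening the wording of 7.2, 8.1 and 10.2.1 and adding a diagnosis column would alter no dose estimate. Either protocol edit needs IRB approval (14.3).

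**The case for a change.** The strongest case for a change is that enrollment is defined by the listed criteria and not by descriptive sections. Listing 16.2.1.2 explains failure of eligibility only by criteria not met or exclusions met, so a non-HCC patient could appear there as fully eligible. The per-protocol set would not clearly help, since it removes major deviations and it is uncertain that one would have occurred. The routes in step 3 work only after enrollment, and no consequence is attached to them. If HCC is already implied, stating it costs a few words and excludes nobody the sponsor meant to enroll.

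Part of this stands. The passages do not agree word for word, the SAP has no explicit handling for a subject without HCC, and a reader is entitled to know whom the results describe. It does not show that the planned analysis would mislead. The primary objective is the absorbed dose of Tc-99m MAA to the whole body and non-liver organs, and it names no diagnosis. All analyses are descriptive. The one case series that Protocol section 5 describes by diagnosis consists of HCC patients, so the documents offer no comparison from which to infer a different dose in others. The argument that stating HCC costs little assumes that HCC is the intended limit, which the documents leave open.

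**Conclusion.** The discrepancy between the population statements and the criteria is genuine but is one of wording, and it does not call for a change to the plan. Its demonstrated effect on the dose estimates is nil: no dose difference by diagnosis and no likelihood of enrolling a non-HCC patient can be taken from the documents. The 20% figure is merely the weight of any one of five patients.

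Analysts can fill the gap sensibly by describing the enrolled patients by diagnosis in the report, from data already collected, and by printing the months-since-diagnosis variable only where it applies.

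This rests on three assumptions: that medical history or the HCC date field reveals each subject's diagnosis, that a blank date is queried, and that subject-level doses are listed as SAP section 11 plans. The judgment would differ if diagnosis were not recorded at all, or if there were evidence in hand that extrahepatic dose depends on it.

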### 8.3. *Exclusion Criteria*

Subjects who meet any one of the following criteria (Table 8.3-1) will be excluded from this clinical study.

**Table 8.3-1: Exclusion Criteria**

Exclusion Criteria	1. Patients who are contraindicated for TheraSphere treatment 2. Patients who are contraindicated for Tc-99m MAA per the applicable Package Insert 3. Patients who do not receive Tc-99m MAA during pre-treatment Y-90 mapping
---------------------------	---

## 9. Subject Accountability

### 9.1. *Point of Enrollment*

Patients who provided written informed consent, meet all inclusion criteria and meet no exclusion criteria are considered enrolled in the study.

### 9.2. *Withdrawal*

Patients may leave the study at any time for any reason and without any consequences. The Investigator or designee will try to obtain the reason for study withdrawal and document this in the source data. An Investigator may discontinue a patient from the study, with or without the patient's consent, for any reason that may, in the Investigator's opinion, negatively affect the well-being of the patient. If a patient is withdrawn from the study, the Investigator will promptly inform the patient and sponsor. Data already collected will be retained and reported; however, no new data will be collected after the withdrawal.

Patients withdrawn from the study for any reason will be asked to participate in a limited capacity by allowing their medical status to be followed by telephone contact, medical chart review, or other agreed upon method. If a patient decides not to continue participation in a limited capacity, the Investigator will not access their medical record or other confidential records for new purposes related to the study; however, study data collected prior to their withdrawal may be reviewed and publicly available records may be consulted prior to or after their withdrawal.

### 9.3. *End-of-Study Definition*

The study will be considered complete after five patients have three post-Tc-99m MAA imaging assessments.

## 10. Study Methods

### 10.1. *Data Collection*

The data collection schedule is shown in Table 10.1-1.

**Table 10.1-1: Schedule of Assessments**

Procedure/Assessment	Study Visit 1: Screening and Enrollment	Study Visit 2: Immediately following Tc- 99m MAA injection	Follow-up Visits	
			Study Visit 3: 4 hours ( $\pm$ 2 hours) following Tc-99m MAA injection	Study Visit 4: $\geq$ 18 hours but $\leq$ 24 hours following Tc- 99m MAA injection
Informed consent process, including informed consent signature date	X			
Inclusion/Exclusion Criteria Assessment	X			
Demographics	X			
Medical history	X			
SPECT-CT		X		
SPECT			X	X
Procedure-related Serious Adverse Events assessment		X	X	X

## **10.2. Study Candidate Screening**

A patient is considered enrolled once an informed consent form has been signed, and all inclusion and no exclusion criteria have been met.

If the patient is found to not meet the inclusion criteria, the patient should not be included in the study, nor should the patient be followed post-procedure per protocol.

